Immunogenicity, SARS-CoV-2-specific bAb and nAb, will be assessed at multiple time points in this study. Mixed effects models will be used to analyze all post-booster/baseline measures. The models will include treatment group, analysis visit, treatment by visit interaction, and adjustment for age groups and pre-booster titer levels. An unstructured covariance structure will be used to

model the within-participant errors. The GMT will be estimated from the model and its corresponding 95% CI will be provided for each group at each post-boost timepoint. The GMR (ratio of GMTs) for mRNA-1273.529 and for mRNA-1273.214 with respect to mRNA-1273 will be estimated from each model and the corresponding 95% CI will be provided at each post-boost time point.

For each of the antibodies of interest (eg, levels of SARS-CoV-2-specific bAb and SARS-CoV-2-specific nAb), the GMT or level with corresponding 95% CI at each time point, and GMFR of post-booster/pre-booster titers or levels with corresponding 95% CI at each post baseline time point will be provided for each arm. The 95% CIs will be calculated based on the t-distribution of the log-transformed values then back-transformed to the original scale for presentation. The following descriptive statistics will also be provided at each time point: number of participants (n), median, minimum, and maximum. PPSI will be used as the analysis population to summarize the immune responses (antibodies of interest) and will the above summary statistics including GMT and GMFR will be provided by pre-booster/study baseline SARS-CoV-2 status.

SRR definitions and analyses will be defined in the SAP.

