6.4.2.1.2. Secondary Analyses

The ANCOVA model described in [Section 6.4.2.1.1](#) will be used for secondary analyses to assess for immune response of mRNA-1273.529 compared to mRNA-1273 booster administered as a 3rd or 4th dose at all measured time points. Antibody titers against the B.1.1.529 strain will be a dependent variable, and a group variable (mRNA-1273.529 and mRNA-1273) will be the fixed effect, adjusting for age groups (≥ 16 to < 65 , ≥ 65 years), most recent COVID-19 vaccination type (mRNA or viral vector) and pre-booster antibody titer level, if applicable. The GMT will be estimated by the GLSM from the model and its corresponding 95% CIs will be provided for each group. The GMR for mRNA-1273.529 with respect to mRNA-1273 will be estimated by the ratio of GLSM from the model and the corresponding 95% CIs will be provided. No hypothesis tests will be performed for these objectives.

For each antibody of interest, the GMT or level with corresponding 95% CI at each time point, and GMFR of post-baseline titers or levels over baseline with their corresponding 95% CIs at each post-baseline time point will be provided. The 95% CIs will be calculated based on the t-distribution of the log-transformed values then back-transformed to the original scale for presentation. The following descriptive statistics will also be provided at each time point: number of participants (n), median, minimum, and maximum. Additionally, reverse cumulative distribution plots and box plots of titers or levels will be generated for each antibody of interest and for any subgroups of interest (e.g., age group).

The mixed effects model repeated measure (MMRM) will be used to analyze all post-booster measures including treatment group, analysis visit, treatment by visit interaction, age groups and pre-booster titer levels (if available) as fixed effects and participant as a random effect. An unstructured covariance structure will be used to model the within-participant errors. The compound symmetry structure will be used when the model fails to converge. The GMT will be estimated from the model and its corresponding 95% CI will be provided for each group at each post-boost timepoint. The GMR for mRNA-1273.529 with respect to mRNA-1273

will be estimated from the model and the corresponding 95% CI will be provided at each post-boost timepoint.

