6.4.2.2.2. Secondary Analyses

The same ANCOVA model described above will be used for secondary analyses to assess for immune response of mRNA-1273.214 compared to mRNA-1273 booster administered as a 4th dose against other variants at Day 29 or Month 3. The GMT will be estimated by the GLSM from the model and its corresponding 95% CIs will be provided for each group. The GMR for mRNA-1273.214 with respect to mRNA-1273 will be estimated by the ratio of GLSM from the model and the corresponding 95% CIs will be provided. No hypothesis tests will be performed for these objectives.

SRR of the mRNA-1273.214 booster administered as a 4th dose against the B.1.1.529 strain, prototype strain and other variants of concern (VOC) will be analyzed in the PPSI-Neg using the methods as described in [Section 6.4.2.1.2](#). A sensitivity analysis of SRR will be performed in the PPSI by using stratified Miettinen-Nurminen method, with pre-booster positive, negative, and unknown SARS-CoV-2 status as strata.

MMRM as described in [Section 6.4.2.1.2](#). will be used to assess immune response mRNA-1273.214 against both the B.1.1.529, the prototype strain, and other VOC at all measured timepoints after study vaccine administration.

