9.2. Appendix B Analysis Visit Windows

Analysis will be summarized using the following analysis visit window for post injection assessments:

Step 1: If the assessments are collected at a scheduled visit, the collected data will be mapped to the nominal scheduled visit.

Step 2: If the assessments are collected at an unscheduled visit, the collected data will be mapped using the analysis visit windows described in [Table 8](#) below. For participants with confirmed COVID-19, unscheduled assessments will be preferably mapped to the visits with respect to the confirmation of COVID-19 (i.e., Illness Visit Day xx) over nominal scheduled visits (i.e., Day xx).

If a subject has multiple assessments within the same analysis visit, the following rule will be used:

- If multiple assessments occur within a given analysis visit, the assessment closest to the target study day will be used.
- If there are 2 or more assessments equal distance to the target study day, the last assessment will be used.

Table 8 Analysis Visit Windows

Visit	Target Study Day	Visit Window in Study Day
Humoral Immunogenicity		
Baseline (Day 1)	1 (Date of Injection)	≤ 1
Day 29 (Month 1)	29	[2, 57]
Day 85 (Month 3)	85	[58, 132]
Day 179 (Month 6)	179	[133, 269]
Day 359 (Month 12)	359	≥ 270
Cellular Immunogenicity (subset of participants in Part 2 only)		
Baseline (Day 1)	1 (Date of Injection)	≤ 1
Day 8	8	≥ 2

9.3. Appendix C Imputation Rules for Missing Dates of Prior/Concomitant Medications, Non-Study Vaccinations and Prior COVID-19 Vaccination

Imputation rules for missing or partial start/stop dates of medication are defined below:

1. Missing or partial medication start date:

- If only Day is missing, use the first day of the month, unless:
 - The medication end date is on/after the date of injection or is missing/partial AND the start month and year of the medication coincide with the start month and year of the injection. In this case, use the date of injection.
- If Day and Month are both missing, use the first day of the year, unless:
 - The medication end date is on/after the date of injection or is missing/partial AND the start year of the medication coincide with the start year of the injection. In this case, use the date of injection.
- If Day, Month, and Year are all missing, the date will not be imputed, but the medication will be treated as though it began prior to the injection for purposes of determining if status as prior or concomitant.

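### The MMRM gives pre-booster titre and age group one coefficient across all visits; adding covariate-by-visit terms is a cheap, minor improvement

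*SAP*

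**What the plan says.** SAP Section 6.4.2.1.2 (Secondary Analyses, Part 1) defines an MMRM for all post-booster measures, "including treatment group, analysis visit, treatment by visit interaction, age groups and pre-booster titer levels (if available) as fixed effects", with participant as a random effect. The covariance is handled as follows: "An unstructured covariance structure will be used to model the within-participant errors", and "The compound symmetry structure will be used when the model fails to converge". A model GMT with 95% CI is reported for each group at each visit, and the GMR "will be estimated from the model and the corresponding 95% CI will be provided at each post-boost timepoint". SAP Section 6.4.2.2.2 carries the model into Part 2 for B.1.1.529, "the prototype strain, and other VOC at all measured timepoints after study vaccine administration".

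Protocol Section 9.6.1 describes the same model: "The models will include treatment group, analysis visit, treatment by visit interaction, and adjustment for age groups and pre-booster titer levels".

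The visit schedule gives four post-booster blood draws for humoral immunogenicity: Days 29, 85, 179 and 359. The analysis set is PPSI-Neg, whose membership is settled visit by visit (SAP Section 5.5), so participants leave it once infected.

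The non-inferiority and superiority decisions use a separate ANCOVA at Day 29 and at Month 3 (SAP Sections 6.4.2.1.1 and 6.4.2.2.1). Each fit has its own coefficients for titre and age.

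**The concern.** A booster lifts titres and they then decline over a year. The regression of post-booster on pre-booster titre may therefore be stronger at one visit than at another, and the same may be true of the age difference. An MMRM without covariate-by-visit terms replaces the visit-specific slopes with one weighted average. The visit-wise ANCOVAs do not impose this, so the two sets of estimates can differ through model misfit as well as through their use of incomplete data.

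Two things are at stake. The first is some precision in the visit GMRs. The second is the accuracy of the model GMTs at late visits: if low pre-booster titre goes with earlier infection, the participants still in PPSI-Neg at Month 12 have higher pre-booster titres, and a wrong slope at that visit shifts the adjusted mean.

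**Working it through.** The plan states no standard error, power or sample size for the MMRM, so there is no figure to reproduce. The assumed SD of ln titre is redacted. The values below are assumptions, shown as ranges.

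**Inputs.** Four post-booster visits (schedule of events); 1:1 allocation; 35% aged 65 or over (SAP Section 6.4.1, Part 1). Assumed: residual SD and pre-booster SD on the ln scale of 1.0 and 1.0, or 0.8 and 1.2. Assumed slopes from Day 29 to Month 12, in equal steps: constant 0.5; mild 0.60 to 0.45; moderate 0.60 to 0.30; steep 0.80 to 0.20.

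**Precision, complete data, unstructured covariance S.** The fitted common slope is b* = (1'S⁻¹b)/(1'S⁻¹1). At visit j, the SE of ln GMR relative to a model with covariate-by-visit terms is √(1 + (b_j − b*)² Var(x)/s_j²).

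- Moderate: b* = 0.45, deviation 0.15 at Day 29 and Month 12. √(1 + 0.0225 × 1) = 1.011; with Var(x)/s² = 1.44/0.64 = 2.25, √(1 + 0.0225 × 2.25) = 1.025.
- Steep: b* = 0.50, deviation 0.30. √(1 + 0.09) = 1.044; √(1 + 0.09 × 2.25) = 1.097.

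| Slopes | SE ratio, Day 29 and Month 12 | SE ratio, Month 3 and Month 6 |
|---|---|---|
| Constant | 1.000 | 1.000 |
| Mild | 1.003-1.006 | 1.000-1.001 |
| Moderate | 1.011-1.025 | 1.001-1.003 |
| Steep | 1.044-1.097 | 1.005-1.011 |

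In the steep case with both SDs 1.0, the Month 12 ratio of 1.044 is worse than with no titre adjustment at all: √(1 + 0.20²) = 1.020.

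For age group, Var = 0.35 × 0.65 = 0.2275. If the age effect drifts from 0 to −0.6 on the ln scale, the largest deviation is 0.30 and the ratio is √(1 + 0.09 × 0.2275) = 1.010. A drift from −0.1 to −0.4 gives 1.003.

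**GMR bias (simulation: 200 per arm, 500 replicates, residual correlation 0.6).**

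- Complete data: largest bias 0.004 on the ln scale; 95% CI coverage 0.94-0.97.
- Titre-dependent exclusion equal in both arms: no GMR bias beyond simulation noise. The Month 12 SE ratio is 1.025 (moderate) or 1.092 (steep).
- Titre-dependent exclusion in one arm only, as a stress case: Month 12 ln GMR bias +0.080, coverage 0.89 (moderate); +0.147, coverage 0.81 (steep). As exp(0.080) = 1.08 and exp(0.147) = 1.16, the GMR is about 8% or 16% too high. The by-visit model stays within 0.003.

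**GMT bias, exclusion equal in both arms.**

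- Heavy exclusion (odds falling e-fold per SD of pre-booster titre, about 54% excluded by Month 12): Month 12 ln GMT bias −0.12, coverage 0.79 (moderate); −0.23, coverage 0.37 (steep). At Month 6 in the moderate case: −0.06, coverage 0.89. The by-visit model has bias of at most 0.007 and coverage 0.93-0.97.
- Lighter exclusion: about −0.07 (moderate) and −0.14 (steep) at Month 12. As 1 − exp(−0.07) = 0.07 and 1 − exp(−0.14) = 0.13, the GMT is roughly 7% or 13% low. The by-visit model is essentially unbiased.

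**The case against.** The strongest reply is that this is a modelling preference with no consequence for the trial's conclusions. Most of that reply stands.

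- Every non-inferiority and superiority decision comes from a visit-specific ANCOVA. The same ANCOVA is also run at all measured time points in Part 1 (SAP Section 6.4.2.1.2) and at Months 6 and 12 in Part 2 (Section 6.4.2.2.3), so unconstrained adjusted GMRs will sit beside the MMRM ones. The MMRM is tied to no hypothesis test, and Month 6 and Month 12 analyses are exploratory (SAP Section 6.6).
- A reader might infer that a constant slope is impossible. The documents do not support that: they report no slope or correlation at any visit, and with a constant slope the loss is zero.
- A reader might also take the MMRM as the plan's check on missing data for Day 29 and Month 3. It is not given that role. SAP Section 6.4.2.3 specifies multiple imputation in the PPSI when more than 10% of the data at Day 29 or Month 3 are missing. Supportive PPSI analyses and an optional Modified PPSI-Neg analysis are also planned.
- Protocol Section 9.6.1 speaks only of adjusting for the covariates, which does not rule out visit interactions. The restriction comes from the SAP's list of fixed effects.

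The reply does not remove two things. The SAP asks for a model GMT with a CI per group and visit, and those GMTs are exposed to titre-dependent exclusion even when the arms behave alike. Exclusion that differs by arm is also conceivable: infection by arm is itself an endpoint, and participants may be unblinded and then boosted outside the study (Protocol Section 6.3.7), which can remove them from per-protocol analysis (Section 6.5.3). Nothing in the documents shows that it occurs.

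**Conclusion.** The point holds as a minor, nearly free improvement. The MMRM constrains the titre and age coefficients to be equal across visits, and nothing in the plan justifies that. If the slope on pre-booster titre weakens over the year, the cost to the GMRs is a small loss of precision at the first and last visits, with intervals that stay valid under the unstructured covariance. The more noticeable effect is on late-visit model GMTs when leaving PPSI-Neg depends on pre-booster titre.

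It would go too far to conclude that the MMRM GMRs are biased in general. That requires titre-dependent exclusion that differs between arms. It would also be wrong to carry the point over to the Day 29 or Month 3 decisions, which do not use this model.

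All sizes rest on assumed slopes, SDs, residual correlation and exclusion patterns. They were worked out for the unstructured covariance, not for the compound symmetry fallback.

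**What to change.** In SAP Section 6.4.2.1.2, add pre-booster titre by visit and age group by visit to the MMRM fixed effects for the 4th-dose groups. State in Section 6.4.2.2.2 that Part 2 uses the same terms, and align the wording of Protocol Section 9.6.1 and the matching synopsis text.

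The cost is 2 covariates × (4 − 1) visit contrasts = 6 extra parameters, against a planned 270-450 (Part 1) or 1328 (Part 2) 4th-dose participants per arm before exclusions. No new data are needed. The terms should not be imposed on the 3rd-dose groups: Part 1 planned only 30-50 per arm, and the protocol's summary of changes says few were randomised.

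Protocol Section 9 requires an amendment for changed methods on primary or secondary objectives, but lets changes to other secondary analyses be listed in the SAP or CSR. The MMRM appears to fall in the latter group, so SAP Section 7, which now lists no changes, is a natural place to record the change and when it was made.

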4.5. Randomization

Randomization will be performed using an interactive response technology (IRT). In Part 1, approximately 600-1000 participants will be randomized in a 1:1 ratio to receive a single dose of either 50 µg of mRNA-1273.529 or 50 µg of mRNA-1273 (active control). In Part 2, approximately 2,924 participants will be randomized in a 1:1 ratio to receive a single dose of either 50 µg of mRNA-1273.214 or 50 µg of mRNA-1273 (active control). In both parts, randomization will be stratified by age groups (16 to < 65 years or ≥ 65 years) and number of booster doses received (to receive study vaccine as the 4th dose or to receive study vaccine as the 3rd dose). At least 90% of participants will receive study vaccine as the 4th dose. There will be four randomization strata for each part:

- ≥ 16 and < 65 years, receive IP as a 4th dose
- ≥ 65 years, receive IP as a 4th dose
- ≥ 16 and < 65 years, receive IP as a 3rd dose
- ≥ 65 years, receive IP as a 3rd dose

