PPSI will be used as the analysis population to summarize the immune responses (antibodies of interest) and the above summary statistics including GMT and GMFR will be provided by pre-booster/study baseline SARS-CoV-2 status.

The SRR is measured by an increase of SARS-CoV-2-specific bAb or nAb titer or value (level) from pre-booster below the lower limit of quantification (< LLOQ) to at least 4 x LLOQ, or a 4-fold or greater rise if pre-booster \geq LLOQ.

The SRR will be summarized at all measured time points for each treatment group with the 95% CI calculated using the Clopper-Pearson method. The difference of SRRs at all measured time points for mRNA-1273.529 compared with mRNA-1273 will be provided with 95% CI using Miettinen-Nurminen method. Analysis of the SRR will be performed in the PPSI-Neg. A sensitivity analysis of SRR will be performed in the PPSI by using stratified Miettinen-Nurminen method, with pre-booster positive, negative, and unknown SARS-CoV-2 status as strata.

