6.4.2.1.3. Exploratory Analysis

Exploratory analyses using the same methods described above will be used to assess for immune response of mRNA-1273.529 compared to mRNA-1273 booster administered against other variant strains (e.g., Alpha, Beta, etc.) after study vaccination. Specifically, for each antibody of interest, the GMT, GMFR and SRR and corresponding 95% CI will be calculated at the time point in which immune response against other variant strains are assessed. Comparisons between booster regimens will be explored by calculating the GMR and differences in SRRs with corresponding 95% CIs, as outlined above.

Exploratory analysis will be performed of the Month 12 immune response using the same methods described above of mRNA-1273.529 compared to mRNA-1273 booster against the B.1.1.529 strain, prototype strain and other variant strains overall and by the Phase B subgroup stated in [Section 6.1](#).

The same ANCOVA model described above may be used for exploratory analyses to assess for immune response of mRNA-1273.529 compared to mRNA-1273 booster administered as a 4th dose against both the B.1.1.529 and the prototype strain at Day 29, using a 95% CI for GLSM and GMR.

Similar analyses will be used to assess for immune response of mRNA-1273.529 compared to mRNA-1273 booster administered against the BA.4/BA.5 variant strains, conducted in the random sample of 200 participants. The exception will be the sensitivity analysis of SRR performed in the PPSI using the stratified Miettinen-Nurminen method, where both SARS-CoV-2 status (positive, negative, and unknown) and age group (≥ 16 to < 65 , and ≥ 65 years) will be included as strata.

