6.4.2.2.3. Exploratory Analyses

Cellular immunity in a subset of participants may be assessed by evaluating the frequency, magnitude, and phenotype of virus-specific T-cell and B-cell responses measured by flow cytometry or other methods, and to perform targeted repertoire analysis of T-cells and B-cells after vaccination.

The same ANCOVA model described above may be used for exploratory analyses to assess for immune response of mRNA-1273.214 compared to mRNA-1273 booster administered as a 4th dose against both the B.1.1.529 and the prototype strain at Day 29, using a 95% CI for GLSM and GMR.

The same ANCOVA model described above will be used for exploratory analyses to assess for immune response of mRNA-1273.214 compared to mRNA-1273 booster administered as a 4th dose against the B.1.1.529 strain, the prototype strain and other variant strains at Month 6 and Month 12 overall and by Phase B subgroup stated in [Section 6.1](#).

Additionally, the SRR will be summarized at Month 6 and Month 12 for each treatment group and by Phase B subgroup with the 95% CI calculated using the Clopper-Pearson method.

Similar analyses will be used to assess for immune response of mRNA-1273.214 compared to mRNA-1273 booster administered against the BA.4/BA.5 variant strains, conducted in the random sample of 200 participants. The exception will be the sensitivity analysis of SRR performed in the PPSI using the stratified Miettinen-Nurminen method, where both SARS-CoV-2 status (positive, negative, and unknown) and age group (≥ 16 to < 65 , and ≥ 65 years) will be included as strata.

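### The secondary seroresponse-rate differences leave out the age stratum used in randomisation, although the titre models adjust for age; the planned interval is valid and the expected gain is small

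*SAP*

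**What the plan says.** SAP 4.5 describes the design for both parts: "randomization will be stratified by age groups (16 to < 65 years or ≥ 65 years"), together with dose number. The secondary SRR objectives concern the 4th-dose group (SAP 2.2.1 and 3.2.1), so dose number is constant there and age is the only stratification factor left.

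The ANCOVA and MMRM models for GMTs adjust for age group (SAP 6.4.2.1.1, 6.4.2.1.2, 6.4.2.2.1).

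For SRR in Part 1, SAP 6.4.2.1.2 gives the method ("The difference of SRRs at all measured time points for mRNA-1273.529 compared with mRNA-1273 will be provided with 95% CI using Miettinen-Nurminen method") and the set ("Analysis of the SRR will be performed in the PPSI-Neg"). The PPSI sensitivity analysis is stratified, but only "with pre-booster positive, negative, and unknown SARS-CoV-2 status as strata".

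For Part 2, SAP 6.4.2.2.2 says SRR "will be analyzed in the PPSI-Neg using the methods as described in" 6.4.2.1.2, and then: "A sensitivity analysis of SRR will be performed in the PPSI by using stratified Miettinen-Nurminen method", again by SARS-CoV-2 status alone.

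Age is an SRR stratum in one place, the exploratory BA.4/BA.5 work. SAP 6.4.2.1.3 reads "The exception will be the sensitivity analysis of SRR performed in the PPSI using the stratified Miettinen-Nurminen method", with SARS-CoV-2 status "and age group (≥ 16 to < 65 , and ≥ 65 years) will be included as strata" in the parallel Part 2 text (SAP 6.4.2.2.3).

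**The concern.** An analysis should normally reflect the factors used to stratify randomisation. Here the continuous comparison of the titres does so and the binary comparison derived from those titres does not, and the SAP gives no reason. Two things could follow.

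- **Precision.** If SRR differs by age, the unstratified variance contains between-age variation that the stratified design has largely removed from the arm comparison.
- **Balance.** PPSI-Neg excludes anyone with evidence of infection up to the analysis visit (SAP 5.5). That happens after randomisation, so the age balance achieved at randomisation need not survive into the analysed set. An unstratified difference does not correct for this.

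What is at stake is how well a descriptive secondary endpoint is estimated, and how easily it can be read beside the age-adjusted GMR. No success criterion is affected.

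**Working it through.** The documents state no SRR, SRR margin, SRR power or interval width, so there is no plan figure to reproduce.

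**Inputs from the documents**
- Allocation 1:1 (SAP 4.5).
- Share aged 65 or over: 35% in Part 1 and 33.5% in Part 2 (SAP 6.4.1).
- 4th-dose participants per arm: 270 to 450 in Part 1 and 1328 in Part 2 (SAP Table 2).

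**Assumptions**
- SRR by age group, shown as a range.
- Evaluable numbers are redacted, so enrolled numbers are used, with half of them (135 and 664) as a check.
- Cochran-Mantel-Haenszel weights for the stratified interval, because the SAP names none.

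**Step 1: variance by hand.** With age shares w_y and w_o, and rates p_y and p_o:
- unstratified variance is proportional to p(1-p), where p = w_y p_y + w_o p_o;
- stratified variance is proportional to w_y p_y(1-p_y) + w_o p_o(1-p_o);
- the difference between them is w_y w_o (p_y - p_o)².

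With w = 0.665 and 0.335:

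| SRR younger / older | Unstratified | Stratified | Variance | Width (square root) |
|---|---|---|---|---|
| 70% / 60% | 0.2223 | 0.2201 | -1.0% | -0.5% |
| 75% / 55% | 0.2165 | 0.2076 | -4.1% | -2.1% |
| 80% / 50% | 0.2102 | 0.1902 | -9.5% | -4.9% |

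**Step 2: full Miettinen-Nurminen 95% intervals**, width unstratified → stratified by age, with age shares equal in the two arms:

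| Assumed SRR, new vaccine vs control (younger/older) | Age gap, points | n = 270 per arm | n = 1328 per arm |
|---|---|---|---|
| 85/85 vs 80/80 | 0 | 0.1289 → 0.1290 (+0.09%) | 0.0578 → 0.0578 (+0.02%) |
| 98/97 vs 97/96 | 1 | 0.0618 → 0.0620 (+0.20%) | 0.0258 → 0.0258 (+0.03%) |
| 85/80 vs 80/75 | 5 | 0.1335 → 0.1334 (-0.06%) | 0.0598 → 0.0597 (-0.16%) |
| 85/75 vs 80/70 | 10 | 0.1378 → 0.1370 (-0.52%) | 0.0617 → 0.0613 (-0.64%) |
| 70/50 vs 60/40 | 20 | 0.1653 → 0.1624 (-1.76%) | 0.0746 → 0.0732 (-1.84%) |
| 75/45 vs 65/35 | 30 | 0.1644 → 0.1576 (-4.17%) | 0.0741 → 0.0710 (-4.27%) |
| 95/65 vs 90/60 | 30 | 0.1302 → 0.1223 (-6.08%) | 0.0578 → 0.0538 (-6.96%) |

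Results at 450 per arm lie between or close to these. At 135 per arm the change is +0.34% to -0.35% for gaps of 0 to 10 points.

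As limits, at 1328 per arm and a 10-point gap, (0.0191, 0.0809) becomes (0.0193, 0.0807).

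**Step 3: validity.** In 1500 simulated trials per setting (n = 270 and 1328; gaps of 0, 10 and 20 points), the unstratified interval covered the true difference in 94.7% to 96.0% of trials. With no age gap, the stratified interval was the narrower one in only about 20% of trials. The simulation drew age counts at random in each arm, so it tests neither stratified allocation nor exclusions that differ by arm.

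**Step 4: imbalance after exclusions.** The crude difference shifts by (difference in share aged 65 or over) × (age gap in SRR). For illustration, with assumed shares of 37% and 33% and a 20-point gap, the shift is 0.04 × 20 = 0.8 points. From Step 2 at 1328 per arm, the standard error is about 0.0746 / (2 × 1.96) = 0.019, or 1.9 points, so the shift is about 0.4 standard errors. Stratifying by age removes it.

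**The case against.** The best defence is that nothing depends on this. SRR carries no hypothesis, margin, alpha or power statement; the objective is to evaluate it. Age is not ignored either. Immunogenicity is assessed within both age groups (SAP 6.1), and age group is summarised in PPSI-Neg (SAP 6.2.2), so an imbalance would be visible. Adding age alone would not give SRR and GMT the same adjustment set, because the ANCOVA also uses pre-booster titre and most recent vaccine type. All of this stands, and it sets the priority low. It does not explain why the one randomisation factor that varies in this group is left out.

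Stratifying also has costs. In the PPSI version, three status levels by two age groups make six strata, and the cell for unknown status and age 65 or over could be sparse. A weighted difference need not equal the difference between the crude arm rates, so the weights must be stated. These points shape the remedy without defeating it.

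A reader might infer two stronger things that the documents do not support:

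- **That the planned intervals are too wide.** This depends on the age gap in SRR, which the documents do not give. With no gap, the stratified interval is very slightly wider.
- **That the SAP contradicts itself because it stratifies by age for BA.4/BA.5.** Age enters only the PPSI sensitivity analysis there; the main BA.4/BA.5 difference follows the same unstratified method. That sample was also drawn with serostatus numbers fixed and the share aged 65 or over set at 35% when feasible (SAP 6.4.1), so its strata match its sampling. It shows that the method is workable here, not that the secondary analysis is in error.

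**Conclusion.** The point holds in a limited form. In both parts the main SRR difference, and its PPSI sensitivity analysis, do not reflect the age factor used in randomisation, while the GMT models for the same titres do. The planned interval is valid and no decision depends on it.

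The gain in width is about nil to 0.6% for age gaps of up to 10 points, about 2% at 20 points and 4% to 7% at 30 points. These figures rest on assumed rates, enrolled numbers and Cochran-Mantel-Haenszel weights. The other benefit is protection against age imbalance after PPSI-Neg exclusions; its size cannot be known from the documents. This is a low-priority improvement.

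**What to change.** - **PPSI-Neg (SAP 6.4.2.1.2 and 6.4.2.2.2):** compute the SRR difference with the stratified Miettinen-Nurminen method, the stratum being age group (16 to under 65, 65 or over). Name the stratum weights, for example Cochran-Mantel-Haenszel.
- **PPSI sensitivity analysis, both parts:** use SARS-CoV-2 status and age group as strata, as already written for the BA.4/BA.5 PPSI sensitivity analysis, with a rule fixed in advance for collapsing sparse strata.
- **Keep** the crude arm-level SRRs with Clopper-Pearson intervals, and note that the stratified difference may not equal their simple difference.

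The cost is a few sentences in the SAP and a change to existing code, with no new data. The documents do not show which SRR analyses have already been run. Where results have been unblinded, report the stratified interval beside the planned one and do not replace it.
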